## 7.4. Positions & Genetic Variations of Interest

### On the nucleotide level:

In the basal core promotor region:

- 1762 and 1764 (Eco numbering will be used)

In the precore region:

- 1896 (Eco numbering will be used)

In the JNJ-3989 binding pocket positions:

- JNJ-3976 (S Trigger)
  - Long list (N=21): 259, 260, 261, 262, 263, 264, 265, 266, 267, 268, 269, 270, 271, 272, 273, 274, 275, 276, 277, 278, and 279
- JNJ-3924 (X Trigger)
  - Long list (N=21): 1779, 1780, 1781, 1782, 1783, 1784, 1785, 1786, 1787, 1788, 1789, 1790, 1791, 1792, 1793, 1794, 1795, 1796, 1797, 1798, and 1799
- In the JNJ-3976/JNJ-3924
- Combination of JNJ-3989 binding site positions JNJ-3976 and/or JNJ-3924

#### Amino acid level:

In the HBV core protein (based on putative binding pocket [[Bourne C. et al., 2006 & Katen S.P. et al., 2013](#)])

- Short list (n=15): 23, 24, 25, 29, 30, 33, 37, 105, 106, 109, 110, 118, 124, 127, 128.
  - Due to an insertion of 12 amino acids in the N-terminal part of core, the 15 HBV Core Protein positions of interest for HBV genotype G are 35, 36, 37, 41, 42, 45, 49, 117, 118, 121, 122, 130, 136, 139, 140

In the pol/RT protein:

- 169, 173, 180, 181, 184, 194, 202, 204, 236, 250

See below breakdown of relative amino acid position of the 10 POI in the RT-domain of polymerase by HBV genotype.

HBV GT-A		HBV-GT-B/C/F/H/I		HBV GT-D		HBV-GT-E/G	
POL number	RT number	POL number	RT number	POL number	RT number	POL number	RT number
517	169	515	169	504	169	514	169
521	173	519	173	508	173	518	173
528	180	526	180	515	180	525	180
529	181	527	181	516	181	526	181
532	184	530	184	519	184	529	184
542	194	540	194	529	194	539	194
550	202	548	202	537	202	547	202
552	204	550	204	539	204	549	204
584	236	582	236	571	236	581	236
598	250	596	250	585	250	595	250

In the major hydrophilic loop of the S-protein region (linked to vaccine escape):

- Amino acids 99 to 169

## 7.5. Analysis Methods

Frequencies and percentages will be presented at the time points specified above for the specified parameters. The denominator is the number of subjects with sequencing data at the selected time point.

A frequency output and/or figure will only be generated if number of participants with respective sequence information available (i.e., baseline sequence info for baseline outputs and paired baseline/post-baseline sequence info for post-baseline outputs) for that respective output or figure is greater or equal to 5 ( $N \geq 5$ ).

For comparison of amino acid or nucleotide levels to universal HBV reference sequences descriptive summaries will be performed by subgroups (HBeAg status at screening and HBV genotypes) by cohort. For comparison of amino acid or nucleotide levels to HBV genotype-specific reference sequences, descriptive summaries will only be performed by HBV genotypes and by cohort.

### 7.5.1. Baseline

The frequency of variant of baseline genetic variations, i.e., the number of subjects with baseline genetic variations, will be tabulated in frequency outputs (n, %), based on NGS data (1% and 15% cut-off), and the genetic variations will be listed for all subjects.

Subgroup analysis by the presence of baseline genetic variations will be tabulated to evaluate the impact on treatment efficacy (efficacy categories including but not limited to functional cure, treatment failure).

### 7.5.2. Post-Baseline

- Time of Virologic Breakthrough (if applicable)

For subjects with virologic breakthrough, the incidence of treatment emergent (NGS) and treatment enriched genetic variations (with primary focus on substitutions) will be tabulated in frequency outputs (n, %) and the genetic variations will be listed for all subjects with paired baseline and post-baseline sequencing data.

The return to baseline for subjects with virologic breakthrough and treatment-emergent genetic variations at time of virologic breakthrough may be tabulated in frequency outputs based on NGS data, as well as the treatment-emergent genetic variations in subjects who did not return to baseline.

- Time of End of Treatment

For subjects who don't meet the NA treatment completion criteria, the incidence of treatment emergent and treatment enriched variants (with primary focus on substitutions) will be tabulated

in frequency outputs (n, %) and the genetic variations will be listed for all subjects with paired baseline and post-baseline sequencing data.

The return to baseline for subjects who don't meet the NA treatment completion criteria and treatment-emergent genetic variations end of treatment may be tabulated in frequency outputs based on NGS data, as well as the treatment-emergent genetic variations in subjects who did not return to baseline.

- Time of Virologic /Clinical Flare (if applicable)

For subjects with virologic/clinical flare, the incidence of treatment emergent (NGS) and treatment enriched genetic variations (with primary focus on substitutions) will be tabulated in frequency outputs (n, %) and the genetic variations will be listed for all subjects with paired baseline and post-baseline sequencing data.

The return to baseline for subjects with virologic/clinical flare and treatment-emergent genetic variations at time of virologic/clinical flare may be tabulated in frequency outputs based on NGS data, as well as the treatment-emergent genetic variations in subjects who did not return to baseline.

- Time of Re-treatment during Post-treatment Follow-up (if applicable)

For subjects who meet re-treatment criteria during follow-up, the incidence of treatment emergent and treatment enriched variants (with primary focus on substitutions) will be tabulated in frequency outputs (n, %) and the genetic variations will be listed for all subjects with paired baseline and post-baseline sequencing data.

The return to baseline for subjects who meet re-treatment criteria during follow-up and treatment-emergent genetic variations at time of meeting the re-treatment criteria may be tabulated in frequency outputs based on NGS data, as well as the treatment-emergent genetic variations in subjects who did not return to baseline.

- Other Post-Baseline

The frequency of variant of genetic variations at other time points will be tabulated in frequency outputs (n, %), based on NGS data (1% and 15% cut-off), and the genetic variations will be listed for all subjects. Time points of specific interest are end-of-treatment, time point of re-treatment, and end-of-study.

### **7.5.3. Over the Study Period**

For all subjects, listings with relevant baseline disease and demographic characteristics, session info, all genetic variations at baseline, at time of virologic breakthrough (if applicable), at end of induction phase, at the end of consolidation phase and at end of FU will be presented.

For all subjects, listings with relevant baseline disease and demographic characteristics, session info, and aggregate post-baseline sequence data over the whole treatment period, and aggregate post-baseline sequence data over the whole study period will be generated.

## 7.6. HBV genotype

Plasma samples for HBV genotyping were taken at screening and tested using the INNO-LiPA HBV genotyping assay. In addition, plasma samples were taken at baseline to determine the HBV genotype using the HBV full genome sequence and phylogenetic analysis.

The number and percentage of subjects by HBV genotype for study analysis will be tabulated. In addition, cross-tabulations per HBV genotype will compare the HBV genotypes determined by the INNO-LiPA HBV genotyping assay and by using the HBV full genome sequence.

## 8. OTHER ANALYSIS

### 8.1. Pharmacokinetics

Descriptive statistics (n, mean, SD, SE, coefficient of variation [CV], geometric mean, median, minimum, and maximum) will be calculated for the plasma or serum concentrations of JNJ-3989 (ie, JNJ-3976 and JNJ-3924) and, optionally, JNJ-6379 NA and/or PegIFN- $\alpha$ 2a, as applicable, and for the derived PK parameters for noncompartmental PK analysis.

For each participant with intensive PK sampling, concentration-time data of JNJ-3976, and JNJ-3924, and optionally JNJ-6379, NA and/or PegIFN- $\alpha$ 2a will be graphically presented. Similarly, graphs of the mean concentration-time profiles and overlay graphs with combined individual concentration-time profiles will be produced. PK parameters in participants undergoing intensive PK sampling will be calculated via noncompartmental methods for JNJ-3976, and JNJ-3924, and optionally of JNJ-6379, NA and PegIFN- $\alpha$ 2a, as applicable. The PK parameters will be  $C_{\max}$ ,  $C_{24h}$ , and  $AUC_{24h}$ . The PK parameters will be subjected to an exploratory graphical analysis, including various transformations, to get a general overview.

To assess the effect of PegIFN- $\alpha$ 2a on JNJ-3989, the PK parameters of JNJ-3976, and JNJ-3924 coadministered with PegIFN- $\alpha$ 2a at Week 8 (or 4) of the consolidation phase will be compared to those of JNJ-3976, and JNJ-3924 at Week 24 (or 28 or 32) of the induction phase as reference. The primary PK parameters are  $C_{\max}$  and  $AUC_{24h}$  on the logarithmic scale. A mixed effects model will be fitted to log-transformed PK parameters with phase (induction or consolidation) as a fixed effect and subject as a random effect.

Special attention will be paid to the concentrations and PK parameters of those participants who discontinued the study for an AE, or who experienced an AE  $\geq$ grade 3 or an SAE.

Population PK analysis of concentration-time data of JNJ-3976, and JNJ-3924, and, optionally, of JNJ-6379, NA and/or PegIFN- $\alpha$ 2a may be performed using non-linear mixed effects modeling. Data may be combined with selected Phase 1 and/or 2 studies to support a relevant structural model. Available participant characteristics (e.g., demographics, laboratory variables, genotypes) will be included in the model as necessary. Details will be given in a population PK analysis plan and results of the population PK analysis, if applied, will be presented in a separate report.

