- kk. PBMC samples will be collected at selected sites only. Additional PBMC samples may be taken in case of ALT flares, upon discussion with the sponsor, and may require an unscheduled visit.
- II. These samples are optional and will only be collected from participants who consent separately to this component of the study. The pharmacogenomic (DNA) sample should preferably be collected at baseline.
- mm. Adverse events and concomitant medications will be monitored from the time a signed and dated ISA ICF is obtained until completion of the participant's last ISA related procedure.
- nn. Exclusion criterion A25 regarding contraindications to the use of PegIFN α2a needs to be checked again at the end of the induction phase prior to the first dose of PegIFN α2a. If a participant's clinical status changes (including any available laboratory results or receipt of additional medical records) after screening but before the first dose of PegIFN α2a is given such that he or she meets exclusion criterion A25, then the participant should continue their study intervention until completion of the consolidation phase without the addition of PegIFN α2a.
- oo. The liver ultrasound does not need to be repeated at baseline if it was done at screening or within 6 months prior to screening.

- pp. As of Protocol Amendment 6, new participants will enroll without randomization to receive JNJ 3989+NA for 36 weeks (induction phase) and will then enter the 12 week consolidation phase during which they will have PegIFN  $\alpha$ 2a added to their treatment regimen.
- qq. Includes close monitoring for neuropsychiatric adverse events during the PegIFN α2a treatment period. Participants who develop a neuropsychiatric adverse event during PegIFN α2a treatment, will be monitored closely until the neuropsychiatric adverse event resolves, with frequent (at least weekly) follow up phone calls.
- rr. Most participants enrolled before Protocol Amendment 6 was in effect, have received JNJ 6379 as part of their study intervention. Dispensation of JNJ 6379 stopped immediately with the removal of JNJ 6379 as study intervention through an urgent safety measure. Participants have to return JNJ 6379 tablets to the site at the next scheduled visit.

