# 2.2.2. Clinical Studies

### 2.2.2.1. JNJ-3989 and JNJ-6379

# Combination of JNJ-3989 and JNJ-6379

Clinical data of triple combination treatment of JNJ-3989, JNJ-6379, and NA are available from the ongoing Phase 1/2a AROHBV1001 study (Cohort 12). Twelve adult chronic HBV mono-infected participants have received 3 subcutaneous injections of JNJ-3989 (200 mg Q4W) in combination with oral JNJ-6379 (250 mg qd) and oral NA treatment (ETV or TDF).

Up to interim analysis cut-off date of 4 October 2019, no deaths, SAEs, or TEAEs leading to study drug discontinuation were reported. Two (16.7%) participants reported at least 1 TEAE during the treatment phase. The TEAEs (upper respiratory tract infection and hypertension) were of mild severity and considered not related to the study drug by the investigator.

The triple combination treatment of JNJ-3989, JNJ-6379, and NA is currently being investigated in chronic HBV mono-infected participants in the ongoing Phase 2 clinical studies 73763989HPB2001 (REEF-1, 90 participants in triple combination Arm 1) and 73763989PAHPB2002 (REEF-2, 80 participants in triple combination Arm 1).

Since the initial protocol writing, interim results of the REEF-1 and REEF-2 studies had become available. In the primary REEF-1 analysis (Week 48, end of treatment) the mean reduction of HBsAg in the triple arm (JNJ-6379+JNJ-3989 100mg+NA) appeared to be less than in the dual arm (JNJ-3989 100mg+NA). More recent interim results of the REEF-2 study (Week 48, end of treatment) confirmed this observation when the effect of JNJ-6379+JNJ-3989 200mg+NA on mean HBsAg level reduction in REEF-2 study is compared to JNJ-3989 200mg+NA in the REEF-1 study. To match with the REEF-2 population, this cross-study comparison focused on the REEF-

1 subpopulation of HBeAg negative, virologically suppressed participants with chronic hepatitis B. PK-PD modelling analyses accounting for variability in baseline characteristics further support this observation. Therefore, a negative effect of JNJ-6379 on the HBsAg lowering effect of JNJ-3989+NA is suspected.

The following sections provide an overview of the current clinical background information for the 2 compounds separately.

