• Prior to Protocol Amendment 5, enrolled participants will enter an induction phase with triple treatment (JNJ-3989]+JNJ-6379+NA) for a response-guided treatment duration of ≥36 weeks to ≤60 weeks. End of the induction phase is defined by either meeting the study defined RGT criterion (HBsAg <10 IU/mL) or reaching study Week 60, whichever comes first. The RGT criterion will be assessed from Week 36 onwards at each study visit, and the assessment will always be based on lab results from the previous study visit. If the RGT criterion is met, the participant will complete the induction phase at that visit and will be randomized in a 1:1 ratio to one of the following intervention arms in the 12-week consolidation phase: JNJ-3989+JNJ-6379+NA+PegIFN-α2a (Cohort 1, Arm 1) or JNJ-3989+JNJ-6379+NA (Cohort 1, Arm 2). At the time of writing Protocol Amendment 5, 22 participants were already enrolled in the study.

*Note:* Participants enrolled before Protocol Amendment 5 is in effect will switch to the new study design as soon as Protocol Amendment 5 is in effect. Participants who did not yet reach the Week 36 visit at that time will have PegIFN- $\alpha$ 2a added to their treatment regimen at Week 36 for 12 weeks. Participants who already passed the Week 36 visit and/or were randomized to the group without PegIFN- $\alpha$ 2a, will have PegIFN- $\alpha$ 2a added to their treatment regimen at the next scheduled visit. After 12 weeks, treatment with PegIFN- $\alpha$ 2a, JNJ-3989 and JNJ-6379 (if applicable) will be stopped.

• Per Protocol Amendment 5, based on the number of participants currently enrolled, it is estimated that approximately 50 participants will be randomized at baseline in a 1:1 ratio to one of the following intervention arms: JNJ-3989+JNJ-6379+NA (Cohort 2, Arm 3) or JNJ-3989+NA (Cohort 2, Arm 4). Upon completion of the 36-week induction phase, all participants will enter the 12-week consolidation phase during which they will have PegIFN-α2a added to their treatment regimen.

*Note*: With the implementation of an urgent safety measure, as described in Protocol Amendment 6, participants previously enrolled had to immediately switch to the new study design. Participants had to stop JNJ-6379 treatment immediately and continue with JNJ-3989+NA treatment up to the end of the induction phase and will then enter the 12-week consolidation phase during which they will have PegIFN-α2a added to their treatment regimen.

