- Per Protocol Amendment #5, participants will be randomized at baseline in a 1:1 ratio to one of the following intervention arms: JNJ-3989+JNJ-6379+NA (Cohort 2, Arm 3) or JNJ-3989+NA (Cohort 2, Arm 4). Upon completion of the 36-week induction phase, all participants will enter the 12-week consolidation phase during which they will have PegIFN- $\alpha$ 2a added to their treatment regimen.

**Note:** With the implementation of an urgent safety measure, as described in Protocol Amendment 6, participants previously enrolled had to immediately switch to the new study design. Participants had to stop JNJ-6379 treatment immediately and continue with JNJ-3989+NA treatment up to the end of the induction phase and will then enter the 12-week consolidation phase during which they will have PegIFN- $\alpha$ 2a added to their treatment regimen.

- As of Protocol Amendment 6, the study will continue as a single-arm study (JNJ-3989+NA+PegIFN- $\alpha$ 2a). All newly enrolled participants will receive JNJ-3989+NA for 36 weeks (induction phase) and will then enter the 12-week consolidation phase during which they will have PegIFN- $\alpha$ 2a added to their treatment regimen.

At the end of the consolidation phase, all participants will enter the FU phase and stop treatment with JNJ-3989+PegIFN- $\alpha$ 2a. If NA treatment completion criteria (HBsAg  $<10$  IU/mL, and HBeAg-negative, and HBV DNA  $<$ LLOQ, and ALT  $<$ 3x upper limit of normal [ULN]) have been met at consolidation Week 12, NA will also be stopped at the next scheduled visit (ie, FU Week 2), otherwise NA treatment will continue during the complete FU phase. Participants will be monitored closely during the 48-week FU phase and should restart NA treatment in accordance with the NA re-treatment criteria.

As of protocol Amendment #6, study intervention consists of:

- 200 mg JNJ-3989 (SC injection Q4W)
- 245 mg tenofovir disoproxil (tablets qd) – **Note:** tenofovir disoproxil may be supplied as fumarate or maleate
- 180 µg PegIFN- $\alpha$ 2a (SC injection, QW)

**Note:** Most participants enrolled before Protocol Amendment #6 was in effect, also received 250 mg JNJ-6379 (tablets qd) as part of their study intervention.

All participants will be considered to have completed the study if they have completed the assessments of the end-of-study (EOS) visit (ie, FU Week 48).

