**Per protocol analysis set (PP):** All participants in the ITT analysis set who do not have any of the selected major protocol deviations that may affect the assessment of efficacy in terms of the primary endpoint at 24 weeks after stopping all study interventions of the consolidation phase. The selected major protocol deviations for efficacy analysis purposes that will be used to identify the participants included in the PP set are described in Section 4.5 and [Attachment 1: Selected Major Protocol Deviations for Analysis Purposes](#). Participants will be analyzed according to the study intervention they were randomly assigned to.

**Pharmacokinetics analysis set (PK):** The PK analysis set is defined as subjects who have received at least 1 dose of any of the study interventions and have at least 1 valid blood sample drawn for PK analysis.

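### The PegIFN effect on JNJ-3989 pharmacokinetics is estimated as a phase effect, which in Cohort 1 may also carry the withdrawal of JNJ-6379

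*SAP*

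**What the plan says.** SAP 8.1 sets out the comparison. The test condition is JNJ-3976 and JNJ-3924 exposure when JNJ-3989 is given together with PegIFN, profiled at consolidation Week 8, with Week 4 as the permitted alternative. The comparator is exposure to the same two components "at Week 24 (or 28 or 32) of the induction phase as reference". Log-transformed Cmax and AUC24h are the primary parameters, and the model is fitted "with phase (induction or consolidation) as a fixed effect and subject as a random effect". Protocol 9.4.3 specifies the same model. Neither text has a term for JNJ-6379, for actual PegIFN use or for cohort.

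The analysis population is not narrowed either. The PK set in SAP 2.3 takes anyone dosed with any study intervention who "have at least 1 valid blood sample drawn for PK analysis", so Cohort 1 is included.

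On JNJ-6379, Protocol 4.1 says that most participants enrolled before Amendment 6 also received 250 mg daily. Under the urgent safety measure, "Participants had to stop JNJ-6379 treatment immediately and continue with JNJ-3989+NA treatment up to the end of the induction phase", after which they were to have PegIFN added.

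On PegIFN, SAP Table 1 gives a consolidation phase even to participants who never received it. Footnote nn of Protocol 1.3.1 says that a participant who meets criterion A25 before the first PegIFN dose "should continue their study intervention until completion of the consolidation phase without the addition of PegIFN". Protocol 4.1 and 7.1 continue JNJ-3989 when PegIFN is stopped early.

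**The concern.** Phase can stand in for PegIFN only if no other relevant co-medication changed between the two PK visits. Under the design before Amendment 5, JNJ-6379 was to be taken in both induction and consolidation, so its background was constant. The urgent safety measure removed that constancy for any Cohort 1 participant profiled on JNJ-6379 in induction and profiled again after the stop.

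The substudy's purpose is to say whether PegIFN changes JNJ-3989 exposure. If JNJ-6379 itself alters that exposure, the planned estimate could report a PegIFN interaction that does not exist, or mask one that does. Elsewhere the SAP does separate participants by JNJ-6379 exposure: in 5.1, 5.3.2 and 5.4.2 for efficacy, and in 6.2.2 for laboratory plots. The PK comparison has no such provision.

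**Working it through.** The documents give no sample size, variability or interaction size for this comparison, so there is no planned figure to reproduce. The check asks what the phase coefficient estimates.

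**Can the stop fall between the profiles?** With a 36-week induction, the default visits are Week 24 and Week 36 + 8 = 44, which are 20 weeks apart. The closest permitted pair is Week 32 and Week 36 + 4 = 40, which are 8 weeks apart. Protocol 2.2.2.1 gives a JNJ-6379 half-life of 93.3 to 110.5 h for single doses of 25 to 300 mg, a range that covers 250 mg. Five half-lives are 5 × 93.3 / 24 = 19.4 days to 5 × 110.5 / 24 = 23.0 days. A reference profile on JNJ-6379 can therefore pair with a test profile washed out of it.

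**What is estimated?** For paired profiles, let P be the true PegIFN ratio, R the ratio of JNJ-3989 exposure with JNJ-6379 to that without it, f the share of pairs on JNJ-6379 at reference and off it at test, and g the share of test profiles without PegIFN. Then

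expected log phase ratio = (1 − g) × ln P − f × ln R.

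**JNJ-6379 term.** Take P = 1, so there is no PegIFN effect, and R from 0.80 to 1.25 (assumed). For example, f = 0.25 and R = 0.80 give −0.25 × ln 0.80 = 0.0558, and exp(0.0558) = 1.057.

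| f (assumed) | R = 0.80 | R = 1.00 | R = 1.25 |
|---|---|---|---|
| 0.10 | 1.023 | 1.000 | 0.978 |
| 0.25 | 1.057 | 1.000 | 0.946 |
| 0.45 | 1.106 | 1.000 | 0.904 |

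The last row uses (60 − 33) / 60 = 27/60. It is the extreme case in which the substudy mirrors the planned enrolment and every participant from before Amendment 6 straddles the stop. The substudy's own mix is not stated.

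**PegIFN term.** With R = 1 and P = 1.25 (assumed), g = 0.10 gives exp(0.9 × ln 1.25) = 1.222, and g = 0.20 gives exp(0.8 × ln 1.25) = 1.195. This applies only if profiles without PegIFN enter as test profiles.

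**Simulation check.** The planned mixed model was simulated with 60 pairs and 60 runs per scenario, assuming between-subject SD 0.3 and within-subject SD 0.2 on the log scale, f = 0.25, g = 0.10 and P = 1. It gave 1.062 for R = 0.80 and 0.943 for R = 1.25, in line with the formula. Keeping only participants with PegIFN at the test profile and adding a time-varying JNJ-6379 term gave 1.004 and 0.997.

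**The case against.** The strongest reply is that the bias needs a JNJ-6379 effect on JNJ-3989 pharmacokinetics, and nothing in the documents shows one. Protocol 2.2.2.2 lists the absence of relevant drug interactions in combination toxicity studies of up to 3 months. That evidence is nonclinical, but it is the only direct evidence given. This stands, and it makes the point conditional. It does not justify leaving the model silent when the background treatment changed by design.

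A reader might infer a pharmacokinetic interaction from the protocol's suspicion of "a negative effect of JNJ-6379 on the HBsAg lowering effect of" JNJ-3989 plus NA. That observation concerns antigen response, not plasma exposure, and does not support the inference.

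A reader might also infer that Cohort 1 Arm 2, randomised to consolidation without PegIFN, contaminates the test profiles. It largely does not. Table 1 starts consolidation at the first PegIFN dose for those who later received it, so their earlier time counts as induction. More generally, SAP 8.1 describes the test condition as JNJ-3989 given together with PegIFN. What remains is participants who meet A25 or stop PegIFN early, in either cohort. For them the intent is clear, but no rule removes or recodes the profile.

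The longer half-life of about 141 h in the protocol should not be used to argue a longer washout, because it comes from a 600 mg dose.

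Finally, SAP section 1 defers PK details to a separate analysis and modelling plan, and SAP 8.2 sends this result to a separate report. An adjustment may exist there. Even so, SAP 8.1 specifies the model, and nothing in the two documents overrides it.

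**Conclusion.** The point holds in a limited form. As written, the phase effect may mix PegIFN addition with JNJ-6379 removal in Cohort 1 pairs that straddle the urgent safety measure. It would go too far to say that the estimate is not the PegIFN effect. It is that effect, apart from changes with time on treatment, if JNJ-6379 leaves JNJ-3989 exposure unchanged or no pair straddles the stop, and if every test profile has PegIFN on board. The number of straddling substudy pairs is unknown, so that any exist is an inference from the design.

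Under the assumed range for R, the distortion is about 2% at f = 0.10, about 5 to 6% at f = 0.25, and about 10% in the extreme case. The objective is exploratory, the substudy is optional, and the documents attach no margin or decision rule to the result. This is a minor improvement.

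**What to change.** In SAP 8.1, and in any separate PK plan:

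- Make the main comparison in participants whose JNJ-6379 status is the same at both PK visits (never exposed, or on it at both). Alternatively, keep all pairs and add JNJ-6379 co-administration at the PK visit as a time-varying fixed effect. An ever/never split is not enough, because status at each profile is what matters.
- Accept as test profiles only those with PegIFN actually co-administered at that visit.
- List the excluded pairs with the reason.
- State that time on treatment remains aliased with PegIFN in this fixed-sequence comparison; neither option removes that.

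The cost is SAP wording. Protocol 6.1 already requires administration of study intervention to be recorded in the CRF, and SAP 4.6 already uses JNJ-6379 and PegIFN administration dates. The downside is that some Cohort 1 pairs may leave the main comparison and reduce its precision.
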